1 INTRODUCTION

1.1 Background

Dry Eye Disease (DED) is often caused by a chronic lack of sufficient lubrication and moisture on the surface of the eye. Consequences of dry eyes range from subtle to constant eye irritation, significant inflammation and even scarring of the front surface of the eye.

Meibomian glands are located in the tarsal plate of the upper and lower eyelids, where they terminate along the interior rim (or margin) of the eyelids. These glands secrete meibum, which is a lipid-rich essential component of a healthy tear film. When sufficient meibum is not present in the tear film, the aqueous layer of the tear film is disrupted and readily evaporates causing irritation, redness, and inflammation of the lid margin and surrounding tissues. Meibomian Gland Dysfunction (MGD) is associated with a failure of these glands to produce adequate quantities of meibum due to atrophy, inflammation, or obstruction and is thought to be the most common cause of evaporative Dry Eye Disease [1; Schaumberg DK 2011].

Initial treatments for the signs and symptoms related to MGD and DED are the use of oil-based artificial tears to supplement the lack of lipid in the tear layer and oral Omega and antiinflammatory prescriptions to decrease inflammation in the soft tissue in the eyelids. Another common treatment is the use of warm compresses applied over the eyelid for extended periods of time, followed by digital massage of the glands by the patient to try and express oil from the meibomian glands. The results of these treatments are often limited and temporary if not continued on a regular basis.

1.2 Study Rationale

Thermal pulsation has been used in clinical settings to provide heat and mechanical stimulation to the eyelids to unblock plugged meibomian glands and reduce symptoms of MGD. Currently there are two FDA cleared thermal pulsation devices; LipiFlow by Johnson and Johnson (K112704) and iLux by Tear Film Innovations, Inc. (K172645). The LipiFlow and iLux systems place a heated plate (40 to 43°C) against the eyelids (Lipiflow on the eyelid conjunctiva) and apply gentle pressure on the lid surfaces. Warming the eyelid tissue softens or melts the meibum, which is known to facilitate gland expression using pressure.

The Tixel device uses heat delivered by a small hot element called the Tip. The device tip is heated during treatment and contacts the skin for a very short period each time it is applied. The Tixel device has been used on the skin area around the eyes to reduce wrinkles, but it has been reported by patients treated with the Tixel that after treatment their eyes feel less dry. The Tixel

system, although applying higher temperature compared with the two predicate devices, is considered to mimic the combination of pressure and temperature effect in a similar manner.

The aim of the current randomized, controlled study is to examine the effect of the Tixel device on the relief of the signs and symptoms of Meibomian Gland Dysfunction (MGD) compared to the FDA approved device, LipiFlow.

1.3 Primary efficacy endpoint rationale

The primary objective of the study is to determine the efficiency of the therapy, in improving TBUT in eyes with DED due to MGD. This objective was chosen because a reduced TBUT is one of the most common signs of DED due to MGD. TBUT is considered abnormal when shorter than 10 seconds. The reason for choosing the margin of 1.5 second as a success criterion is following the recent IPL study performed by Lumenis and received an FDA approval. In the study the difference between the IPL arm and the control arm was 1.24 second. The IPL arm was 1.99 second in combination with MGX, and the sham +MGX was 0.75 meaning that the IPL alone was responsible to 1.24 second from baseline to 4 weeks follow-up (Effectiveness of Intense Pulsed Light for Improving Dry Eye Syndrome - Study Results - ClinicalTrials.gov).

Novoxel

Synopsis -Clinical Protocol Number: CLN 0798 Rev. 002

June 21, 2021

2 THE INVESTIGATIONAL DEVICE

2.1 Device description

Tixel C (Novoxel[®], Israel) is a thermomechanical system developed for fractional treatment. The system is designed for the treatment of soft tissue by direct conduction of heat, enabling tissue coagulation combined with micro ablation with low thermal damage to the surrounding tissue.

Figure 1 - The Tixel C Console and Handpiece Configuration

The system consists of a handpiece connected to a console (Figure 1). The handpiece applies a therapeutic element, the "tip", fixated on the distal section. The tip is comprised of a gold-plated copper base and a thin-walled titanium alloy cover (Figure 2)

[figure not shown]

Figure 2 - The Tixel Small Tip

The handpiece is equipped with a precise motion system based on a linear motor and a digital signal processing (DSP) motion controller. The system design enables precise pre-set periods of skin contact duration. The active surface of the Tixel small Tip consists of an array of 24 (6x4) square-based pyramids evenly spaced within a boundary area of 0.30cm². The pyramids are 1.25mm tall with a flat rectangular apex of approximately 0.01mm². The blunt apex of the pyramid allows effective heat transfer and prevents mechanical puncturing of the skin. The backplane of the tip attaches to a ceramic heater that maintains a Tip base temperature of 400°C during the treatment. The heating enables effective self-sterilization before and during treatment, significantly reducing the risk of cross-contamination from the tip. When the handpiece is not activated, the tip is safely retracted to its home position. When the user activates the handpiece, the linear motor rapidly advances the tip which comes in brief contact with the tissue, and then pulls it back. Thermal energy is transferred to the skin, creating tissue micro ablation and tissue coagulation. The tip recedes within a precisely controlled distance and time to its home position. The duration of the pulse, defined as the time of contact between tip and skin, ranges from 5ms to 16ms.

A second system parameter is the travel or "protrusion" of the tip. Protrusion is defined as the distance that the tip travels from the distal edge of the handpiece (which also functions as a distance gauge). The protrusion adjustment, measured in micrometres (μ m), is designed to ensure good thermal coupling between the tip and the tissue. Adequate combined settings of the two parameters, pulse duration and protrusion, contribute to the desired thermal effect followed by the clinical outcome.

2.2 Safety Features of the Tixel C

-The device tip base temperature is maintained at 400°C, but the dermal thermal lesion under the specified operation parameters is limited to 250μ m (for eyelid treatment parameters), while eyelid thickness varies between 500-1500 μ m. Therefore, there is no risk related to the Tip temperature to the eyelid muscles or meibomian gland or to the eye (sclera or cornea) as shown in pre-clinical and human body histology.

-When the device is contacting the skin for extremely short periods of time, the maximal tissue temperature creating micro ablation is lower than 150°C. The pressure applied by the tip during contact is limited to gently "compress" the eyelid surface resulting in negligible pressure on the eye as shown in laboratory tests.

-The device is IEC-60601 certified (both safety and EMC tests).

-Tixel is approved for use as a medical device by the FDA (The previous version of the Tixel C equipped with the same handpiece and Tip assembly) European Union, Australia, Brazil, South Africa, South Korea, Taiwan Thailand, Israel, among other countries.

-Two clinical studies of the Tixel treatment of peri-orbital wrinkles have received IRB approvals (3 clinical sites in the US and 3 clinical sites in Israel). One study was completed without any related AEs and only 2 patients with AEs in total (5.9%) in the Tixel group. A second study is under process.

-The Tixel device is designed with core safety, which is ensured via several aspects of its components:

-The device has an over-temperature automatic thermal shutdown in case of undesired temperature rise. This component is strictly hardware based.

-In case of a power fail, the tip will always be retracted backwards to its home position.

-The system is always in a rested (home) position and activated only when the trigger is pressed.

-An air-cooled system which does not contain any type of cooling liquid such as water.

-Mechanical BIT (Built-In Test). Before commencing operational mode, the system verifies free motion of the mechanical system.

3 LIPIFLOW® SYSTEM

The LipiFlow System is a medical device intended for use by Eye Care Professionals (ECP) to apply localized heat and pressure therapy to a patient's eyelids. It is cleared to be marketed by the United States Food and Drug Administration and will be used as the control device in this study.

3.1 LipiFlow Indications for Use

The LipiFlow System is indicated for the application of localized heat and pressure therapy in adult patients with chronic cystic conditions of the eyelids, including meibomian gland dysfunction (MGD), also known as evaporative dry eye.

3.2 LipiFlow Components

The LipiFlow Console provides the user interface and control elements of the system, including software, algorithms and control elements (Figure 3).

Figure 3 - The LipiFlow Console and Activator disposable

The Activator, a single-use sterile device, delivers automated therapeutic energies to each meibomian gland. Its contoured design vaults the cornea and protects the eye allowing a maximum therapeutic temperature of 43 degrees Celsius to reach glands from the inner eyelid, without damaging the eyelid or delicate structures of the globe. Insulation protects the cornea from exceeding a safe 39.5 degrees Celsius, while a pressure feedback loop sends pulsed

sequences to expel blockages. Force equalization protects the globe from pressure transmission by focusing energy only on the eyelid. Delivered through the LipiFlow Activator, Vectored Thermal PulseTM (VTP) technology applies a combination of heat and pressure to the inner eyelid to safely remove gland obstructions and stagnant gland content. Vectored heat and adaptive force equalization targets the pulse, heat, and pressure on the meibomian glands to maximize effectiveness. Therapeutic motion provides proximal-to-distal parastalsis to clear gland contents.

4 CLINICAL STUDY DESIGN

4.1 **Objective**

The objective of this study is to evaluate the safety and effectiveness of the Tixel device in adults with meibomian gland dysfunction (MGD).

4.2 Description of the Study

This study is a randomized, open-label, pilot clinical study comparing the Tixel device to an active control, which will be the LipiFlow System. The goal of this study is to compare between the Tixel device and the LipiFlow System and estimate the magnitude of the differences, if they exist, in terms of safety and effectiveness. A total of up to 30 patients (60 eyes) will be randomized for bilateral treatment and will be assigned in a 1:1 ratio into the Tixel treatment group or the control group at up to 2 study sites in Israel and/or Europe. The evaluator will be masked as to the randomization assignments. Both eyes will receive the same randomized assignment and both eyes of each patient will be evaluated at all time points. One eye will be selected as the designated "study eye" for statistical purposes: The study eye is the eye with the lower baseline TBUT. If both eyes have the same TBUT, the right eye will be the study eye. Outcome Measures

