4.2.1 Primary Effectiveness Endpoint

The primary effectiveness endpoint is the change from baseline to the 4-weeks follow up exam in Tear Break-Up Time (TBUT). TBUT must be assessed by a masked rater. The changes from baseline will be evaluated.

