5.1 Inclusion Criteria

- 1. Age 18 years and older of any gender or race.
- 2. Provision of written informed consent prior to study participation.
- 3. Willingness and ability to return for all study visits.
- A positive history of self-reported dry eye symptoms for three months prior to the study using the Ocular Surface Disease Index (OSDI) questionnaire, and a score of ≥ 23 at the baseline visit.
- Evidence of meibomian gland (MG) obstruction, based on a total Meibomian Gland Score (MGS) of ≤12 in the lower eyelids for each eye. The rater of MGS must not be involved in the study procedure.
- 6. Non-invasive tear break-up time (TBUT) <10 seconds in both eyes. The rater of TBUT must not be involved in the study procedure.
- 7. Agreement/ability to abstain from dry eye/MGD medications for the time between the treatment visit and the final study visit. Ocular lubricants are allowed if no changes are made during the study.
- 8. Fitzpatrick skin type I-VI.

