Slit Lamp for Anterior	Using biomicroscopy to examine anterior segment including
Segment Health	lids, adnexa, conjunctiva, sclera, corneal clarity, and surface
	integrity, anterior chamber, and iris. Grading system:

Table 1-Patient Assessments

	• 0=No clinical findings
	• 1=Non-clinically significant positive findings (including
	pterygium, pinguecula, corneal scar, conjunctival pigment,
	corneal arcus, verucca, non-visual significant lens changes)
	• 2=Abnormal findings
Lid Margin Abnormalities	Scored 0-4 based on the number of the following present in
	each eye:
	• irregular lid margin
	• vascular engorgement
	plugged meibomian gland orifices
	• anterior or posterior replacement of the mucocutaneous
	junction
Eyelid Margin Assessment	Development of any of the following: • entropion or ectropion
	• floppy eyelids • loss of lash integrity
Tear Break-Up Time	Note: TBUT Assessments must be made by a rater not
(TBUT)	involved in the study procedure and blinded to the arm to
	which the patient is randomized
	• Use one Fluorescein strip per eye
	• Apply one or two drops of non-preserved saline to
	the impregnated paper tip. Excess fluid will
	automatically fall off. Shaking is neither required nor desirable
	 Ask the patient to look down and in
	• Gently touch the strip to the superior temporal bulbar
	conjunctiva for one or two seconds
	Ask the patient to blink three times and open eyes neturally
	naturallyImmediately measure the time between the last blink
	and the first appearance of a dark spot on the cornea
	(formation of dry area)
	• Time shall be recorded in seconds and shall be the
	average of three consecutive measurements Period average of three consecutive measurements
	• Repeat with a new strip for the second eye

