6.5 Treatments

The study procedure in both study arms shall be performed on both eyes on the same day.

Testing must be done in the following order:

- Concomitant systemic and ophthalmic medications (before treatment 1, only if not done during screening).
- Patient's report of the daily usage (frequency and dose) of eye lubricants. Before treatment 1, only if not done during screening. If data was collected at screening, only changes will be collected.

Before treatments 2 and 3 in the Tixel arm- patient's report will be collected since the last treatment done.

Before treatment 1, only for 10 patients randomized to a sub-set of the Tixel arm: Cornea
OCT and coded images upload to EDC and/or SharePoint. OCT assessment should be
performed before any corneal testing.

The following tests may be done again before treatment #1, only if treatment is being done on a different day than baseline exam, at the discretion of the investigator (these tests will be done prior to treatments 2 and 3 for the Tixel arm):

- Slit Lamp for Anterior Segment
- Lid Margin Abnormalities
- Eyelid Margin Assessment
- 1. Eye makeup shall be removed.
- The device shall be prepared for use in accordance with the Instructions for Use (IFU)/User Manual for the device to which the patient is randomized. An IFU/User Manual is packaged with each device that will be used in the study.
- For the LipiFlow treatment- Anesthetic eye drops shall be applied as per the Testing Methodologies for CLN 0798 study (CLN_0802).
- 4. For the Tixel treatment-Anesthetic cream/gel may be applied only on the eyelids according to the investigator discretion.
- Therapy shall be delivered in accordance with the IFU/User Manual for the device to which the patient is randomized. Refer to the Testing Methodologies for CLN 0798 study (CLN_0802) for more information.
- 6. For Tixel device treatment, the following zones will be treated at the following Parameters: Small tip, 6 milliseconds pulse duration, 400μm protrusion, single pulse in the following order:
 - 5 shots nasal, medial, temporal region directly below/above lid margin next to each other (Figure 4)
 - 5 shots a little lower/higher (Figure 4)

Figure 4-Treatment Zones With Tixel

7. Representatives from the Sponsor may be present during the study visits when required.

- 8. Throughout the treatment visit, patients will be assessed for any adverse events, including for development of entropion or ectropion, floppy eyelids, and lash integrity assessment.

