7 STATISTICAL CONSIDERATIONS

7.1 General Considerations

Descriptive statistics will be used to summarize continuous variables (number of eyes/patients [N], mean, standard deviation (SD) or standard error of the mean, median, maximum, and minimum) and categorical variables (frequency and percentage) at each assessment timepoint. Statistical comparisons within each group will be performed using appropriate statistical methods or models, and the results such as 95% confidence intervals and p values will be reported. All summary tables will be supported with individual patient and eye data listings. Baseline is defined as the last non-missing observation prior to initiation of study intervention. Analyses will be carried out using SAS software or equivalent statistical software.

Further details will be described in the statistical analysis plan, which will be finalized prior to the study database lock.

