7.4 Effectiveness Analyses

- Primary endpoint

The change from baseline at 4 weeks in TBUT in both study arms will be calculated along with 95% confidence interval. The Paired T-test or Signed rank test for two means (paired observations) (as is appropriate) will be applied for testing the statistical significance of the change within each study group.

Ho: $\mu h - \mu c < 1.5$

HA: $\mu h - \mu c \ge 1.5$

where μ 4w and μ base are the mean at 4 weeks and at baseline, respectively.

- Secondary effectiveness endpoints
- The change from baseline in the TBUT at 4 weeks will be analysed for non-inferiority with a margin of 1.5 using a one-sided two-sample t-test. The non-inferiority hypothesis set will be:

Ho: $\mu h - \mu c > 1.5$

HA: $\mu h - \mu c \leq 1.5$

where μ t and μ c are the mean changes from baseline for Tixel and control, respectively. Thus, the upper limit of the two one-sided 97.5% CI must be < 1.5 in order to demonstrate Tixel non-inferiority.

- The change from baseline at 12 weeks in TBUT will be calculated along with 95% confidence interval. The Paired T-test or Signed rank test for two means (paired observations) (as is appropriate) will be applied for testing the statistical significance of the changes within each study group.
- The change from baseline at 4 weeks and 12 weeks in the Ocular Surface Disease Index (OSDI) will be calculated along with 95% confidence interval. The Paired T-test or

Signed rank test for two means (paired observations) (as is appropriate) will be applied for testing the statistical significance of the changes within each study group.

• The change from baseline at 4 and 12 weeks in the MGS score will be calculated along with 95% confidence interval. The Paired T-test or Signed rank test for two means (paired observations) (as is appropriate) will be applied for testing the statistical significance of the change within each study group.

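### Choosing the study eye by its lower baseline TBUT biases the within-arm change upward, by an amount the documents do not fix (near 0 to about 0.76 s)

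*Combined protocol and SAP*

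**What the plan says.** Section 4.2 names one eye per patient for the statistics: "The study eye is the eye with the lower baseline TBUT", with the right eye taken in a tie. It also says that "both eyes of each patient will be evaluated at all time points", and both eyes receive the same device.

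Section 4.2.1 sets the endpoint: "The primary effectiveness endpoint is the change from baseline to the 4-weeks follow up exam in Tear Break-Up Time (TBUT"). Section 7.1 adds: "Baseline is defined as the last non-missing observation prior to initiation of study intervention". Section 6.5 introduces its pre-treatment repeats with "The following tests may be done again before treatment #1, only if treatment is being done on a different day than baseline exam"; the list holds slit lamp, lid margin abnormalities and eyelid margin assessment, not TBUT. On that text, the reading that selects the eye is also the reading subtracted.

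The primary analysis in section 7.4 is a paired t-test or signed rank test, for "testing the statistical significance of the change within each study group". The comparison of TBUT change between arms is a secondary non-inferiority analysis. Section 7.7 sizes the trial on the paired test: 15 per group, change 1.5 s, SD of differences 1.9 s, two-sided 0.05.

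Entry under section 5.1 requires "Non-invasive tear break-up time (TBUT) <10 seconds in both eyes". No section averages the two eyes, takes a fresh baseline after the eye is chosen, or otherwise allows for regression to the mean.

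**The concern.** The lower of two noisy readings tends to be low partly because of the noise. When that reading is both the selection criterion and the baseline, the next reading of the same eye is higher on average even if nothing has changed. A between-arm contrast would cancel this in expectation; a paired test within one arm cannot, and the trial has no sham or untreated arm.

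At stake are the estimated TBUT change in each arm, which would be too large, and the error rate of the primary test if it is made against zero. The estimate also matters because section 1.3 treats 1.5 s as the mark of success and because a pilot's effect sizes tend to be carried forward.

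The selection is not needed. Both eyes must qualify on TBUT, both are treated alike, and both are measured at every visit.

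**Working it through.** **Plan's own figure.** Paired t-test, n = 15, effect size 1.5/1.9 = 0.789, two-sided 0.05, noncentral t: power 81.1% (80.2% at the printed 0.78). The smallest n for 80% is 15. Section 7.7 reproduces, and it is a test against zero.

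**Inputs from the documents.** n = 15 per arm; SD of change 1.9 s; alpha 0.05 two-sided, so 2.5% on the improvement side.

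**Inputs assumed.** The documents do not split the variance of TBUT. Treat the 1.9 s as visit noise only, so the noise variance per reading is 1.9²/2 = 1.805 s² (SD 1.34 s). Let f be the share of that variance specific to one eye, the rest being common to both eyes at a visit. Let s_eye be the SD of each eye's true deviation from the patient's mean. True treatment effect is zero.

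**Formula.** With s_e² = f × 1.805, the expected spurious change from taking the lower eye is s_e² / √(π(s_eye² + s_e²)).

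- Upper end, f = 1, s_eye = 0: 1.805/√(π × 1.805) = 0.758 s, or 51% of 1.5 s.
- Mid case, f = 0.5, s_eye = 0.7: 0.9025/√(π × (0.49 + 0.9025)) = 0.43 s, or 29%. With s_eye = 1.0 it is 0.37 s.
- Low case, f = 0.25, s_eye = 2.0: 0.451/√(π × (4 + 0.451)) = 0.12 s, or 8%.
- Lower limit, f = 0: 0 s.

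**Chance of a false significant improvement, test against zero.** Noncentrality is bias/1.9 × √15, with a critical t of 2.145 on 14 degrees of freedom.

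| Bias (s) | Noncentrality | Upper-tail rejection |
|---|---|---|
| 0 | 0 | 2.5% |
| 0.12 | 0.25 | 4.2% |
| 0.37 | 0.75 | 10.4% |
| 0.43 | 0.88 | 12.7% |
| 0.758 | 1.55 | 30.2% |

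**Simulation, zero effect, 20,000 trials of 15.** With f = 0.5 and s_eye = 0.7, the lower-eye rule gave +0.425 s and 12.9% upper-tail rejection. Always taking the right eye gave 0.00 s and 2.5%. The two-eye mean gave 0.00 s and 2.4%, and its SD of change was 1.65 s against 1.85 s for the lower eye. Selection trims the SD a little, so the table is approximate at the top: with f = 1 and s_eye = 0.7, the simulated SD was 1.77 s and rejection 28%, against 25% from the formula at SD 1.9 s.

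**Test against 1.5 s.** The standard error is 1.9/√15 = 0.49 s. Even at the upper-end bias, rejection in favour of a change above 1.5 s is about 0.04%. The observed mean would reach 1.5 s about 7% of the time at the upper end and about 1.5% of the time at +0.43 s.

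**Entry limit.** Adding the <10 s limit on the same reading (f = 0.5, s_eye = 1.0, assumed between-patient SD 2 s), the lower-eye rule gave +0.51 s and 17% when mean TBUT was 7 s; always taking the right eye still gave +0.17 s and 5%. With mean TBUT 5 s, the figures were +0.36 s and 0.00 s.

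**The case against.** The strongest reply is that the randomized comparison is untouched. The eye is chosen by the same rule in both arms, so the artefact is equal in expectation and cancels in the between-arm analysis, and section 4.2 gives comparison of the two devices as the goal of a pilot. That stands. It does not protect the primary test, which is within arm.

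Second, the size is uncertain. Both eyes are read at one visit, and tear state, environment and lubricant use may move them together; shared error produces no selection bias. This stands, and it is why the range starts near 0. Each reading is also the "average of three consecutive measurements" (Table 1, section 6.2), but these are taken at one sitting, which reduces within-session error and not variation between visits.

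Third, a reader might infer that an inert device could meet the trial's primary criterion. The documents do not settle that. The hypotheses printed under the primary endpoint in section 7.4 use 1.5, with symbols that do not match their definitions, while section 7.7 tests against zero. Only the test against zero is inflated.

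Fourth, Appendix A, the schedule of events, is not in the text available, so a second TBUT before treatment cannot be excluded; section 6.5 lists none. Section 5.1 calls the entry TBUT non-invasive while Table 1 describes a fluorescein method. If these are separate readings, the entry limit contributes less regression, but the eye-choice effect remains if the eye is chosen on the reading that is subtracted.

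**Conclusion.** The point holds in direction: under the text available, the lower-eye rule biases the within-arm TBUT change upward in each arm whenever there is eye-specific error. Its size is not determinable from the documents: near 0 s to about 0.76 s, with about +0.4 s as a mid case. At n = 15 and SD about 1.9 s this corresponds to about 2.5% to 30% false significant improvement in a test against zero, about 13% in the mid case. The top of the range needs all of the planned SD to be independent eye noise and no true difference between eyes.

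Three stronger readings are not supported. A false-positive rate of 23% can be obtained for the same +0.43 s, but only with an SD of change of 1.27 s; at the planned 1.9 s it is 12.7%. The secondary non-inferiority comparison is not biased in expectation. The argument does not carry over to MGS, because the eye is selected on TBUT.

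This should be fixed. It does not invalidate the design, but it adds an avoidable bias to the primary estimate.

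**What to change.** In sections 4.2 and 7.4, and in the SAP, define the TBUT analysis variable as the per-patient mean of both eyes at baseline and at each follow-up. This keeps one value per patient and n = 15 per arm. Alternatively, fix the study eye without reference to baseline TBUT, for example the right eye for all. Keep the lower-TBUT-eye result as a supportive analysis. State in section 7.4 whether the primary test is against zero or 1.5 s, since the consequence depends on it, and confirm in Appendix A whether any second TBUT precedes treatment.

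The cost is wording: no added patient, visit or measurement. Averaging also lowers the SD of change unless the two eyes share all their error. The reported mean change will probably be smaller. Some regression from the <10 s entry limit may remain: with assumed mean TBUT of 7 to 8 s, noise SD 1.34 s and half the error shared, averaging leaves about +0.16 to +0.26 s and 5% to 8% false positives. The report should therefore not attribute the within-arm change to the device on its own.
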